- p. Patients receiving medications (within the last 6 weeks prior to baseline [visit 2, day -1]) that have been proven to prolong QT interval or who may require such medications during the course of the study such as, but not limited to, non-allowed anti-psychotic medications, tricyclic antidepressants and/or Class I antiarrhythmics.

- q. Patients receiving medications (within the last 6 weeks prior to baseline [visit 2, day -1]) that are metabolized by CYP2D6 and have the potential of reducing seizure threshold.
- r. Creatinine clearance <60 mL/min at screening, calculated using the Cockcroft-Gault equation: $(140 - \text{age}) \times \text{mass (kg)} / 72 \times \text{serum creatinine (mg/dL)}$. It is allowed to repeat the test once, if clinically appropriate.
- s. Any clinically significant, abnormal, screening laboratory result, which in the opinion of the investigator, affects the patients' suitability for the study or puts the patient at risk if he enters the study.
- t. Alcohol and/or drug abuse within the 6 months prior to screening, as defined by the DSM-5 (American Psychiatric Association 2013).
- u. Patients with adverse events of suicidal ideation or attempt at any time in the past or as measured by suicide ideation score of ≥ 3 on the C-SSRS (screening version), or patients who answer "Yes" on any of the 5 C-SSRS Suicidal Behavior Items (actual attempt, interrupted attempt, aborted attempt, preparatory acts, or behavior) if the attempt or acts were performed at any time in the past, or patients who, in the opinion of the investigator, present a risk of suicide.
- v. Patients with known intracranial neoplasms, vascular malformations, history of cerebrovascular accident, or intracranial hemorrhage.
- w. Current or history of clinically significant allergy or known hypersensitivity to any ingredients of the study medication [REDACTED]
- x. Treatment with tetrabenazine within 6 weeks of study baseline (visit 2, day -1).
- y. Treatment with any investigational product within 6 weeks prior to the first day of study drug administration or within 5 half-lives (whichever is longer) or patients planning to participate in another clinical study assessing any investigational product during the study.
- z. Use of one of the following prohibited substances, or foods as follows:

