- j. Creatinine clearance <90 mL/min at screening, calculated using the Cockcroft-Gault equation. It is permitted to repeat the test once, if clinically appropriate.
- k. Hemoglobin value below the lower limit of the reference range and evaluated by the investigator to be clinically significant.
- l. Positive serology for HIV-1, HIV-2, HBsAg, and/or hepatitis C.
- m. Presents or has a history of clinically significant diseases of the renal, hepatic, gastrointestinal, cardiovascular, musculoskeletal, immunological, endocrine (including diabetes even if controlled by diet), metabolic diseases, or other condition known to interfere with the absorption, distribution, metabolism or excretion of drugs, as judged by the investigator.

- n. History of alcohol, narcotic, or any other substance dependence in the past 2 years, as defined by the Diagnostic and Statistical Manual of Mental Disorders, Fifth Edition (DSM-5, [American Psychiatric Association 2013](#)).
- o. History of clinically significant psychiatric diseases, such as major depressive disorder or anxiety, as judged by the investigator.
- p. Subjects with adverse events of suicidal ideation or attempt at any time in the past or as measured by suicide ideation score of ≥ 3 on the C-SSRS (screening version), or subjects who answer “Yes” on any of the 5 C-SSRS Suicidal Behavior Items (actual attempt, interrupted attempt, aborted attempt, preparatory acts, or behavior) if the attempt or acts were performed at any time in the past, or subjects who, in the opinion of the investigator, present a risk of suicide.
- q. Has had one of the following conditions:
 - major trauma or surgery in the 2 months before screening or at any time between screening and admission
 - acute/chronic infection within 2 weeks before screening or at any time between screening and admission
 - malignancy within the last 5 years
 - epilepsy, seizure, convulsions or syncope (including febrile seizures)
 - history of tuberculosis
 - BP outside the range of 90 to 139 mmHg (systolic) or 55 to 89 mmHg (diastolic); or pulse rate outside the range of 45 to 99 bpm; all measured after 5 minutes rest in seated or supine position. Vital signs may be retested twice at intervals of 5 minutes.
- r. Not willing or able to refrain from intensive physical exercise during the study.
- s. Current or history of clinically significant allergy or known hypersensitivity to any ingredients of the study medication [REDACTED]

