- p. Patients receiving medications (within the last 6 weeks prior to baseline [visit 2, day -1]) that have been proven to prolong QT interval or who may require such medications during the course of the study such as, but not limited to, non-allowed anti-psychotic medications, tricyclic antidepressants and/or Class I antiarrhythmics.
- q. Patients receiving medications (within the last 6 weeks prior to baseline [visit 2, day -1]) that are metabolized by CYP2D6 and have the potential of reducing seizure threshold.
- r. Creatinine clearance <60 mL/min at screening, calculated using the Cockcroft-Gault equation: $(140 - \text{age}) \times \text{mass (kg)} / 72 \times \text{serum creatinine (mg/dL)}$. It is allowed to repeat the test once, if clinically appropriate.
- s. Any clinically significant, abnormal, screening laboratory result, which in the opinion of the investigator, affects the patients' suitability for the study or puts the patient at risk if he enters the study.
- t. Alcohol and/or drug abuse within the 6 months prior to screening, as defined by [DSM-5 \(American Psychiatric Association 2013\)](#).
- u. Patients with adverse events of suicidal ideation or attempt at any time in the past or as measured by suicide ideation score of ≥ 3 on the C-SSRS (screening version), or patients who answer "Yes" on any of the 5 C-SSRS Suicidal Behavior Items (actual attempt, interrupted attempt, aborted attempt, preparatory acts, or behavior) if the attempt or acts were performed at any time in the past, or patients who, in the opinion of the investigator, present a risk of suicide.
- v. Patients with known intracranial neoplasms, vascular malformations, history of cerebrovascular accident, or intracranial hemorrhage.
- w. Current or history of clinically significant allergy or known hypersensitivity to any ingredients of the study medication [REDACTED]
- x. Treatment with tetrabenazine within 6 weeks of study baseline (visit 2, day -1).
- y. Treatment with any investigational product within 6 weeks of screening prior to the first day of study drug administration or within 5 half-lives (whichever is longer) or

patients planning to participate in another clinical study assessing any investigational product during the study.

z. Use of one of the following prohibited substances, or foods as follows:

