4.3. Justification for Key Inclusion and Exclusion Criteria

The majority of participants enrolled in this study will be healthy subjects; therefore, the inclusion/exclusion criteria established for this trial are those typically utilized to define this population. Due to unknown potential effects of the ^{18}F -tracers on a developing fetus, women have been excluded from participation in the trial, and male subjects must agree to use contraception for the duration of the trial and for 90 days after discontinuation of the study drug.

[REDACTED]

[REDACTED], subjects with current or history of a heart condition or increased pro-arrhythmic risk, epilepsy or seizures within the last 5 years, and clinically significant psychiatric diseases such as major depressive disorder or anxiety are to be excluded from participation in this study.

All subjects participating in this study will receive multiple scans (MRI and PET); therefore, individuals with a history of claustrophobia will be excluded from participation in this study. Additionally, subjects may not have contraindications to MRI such as the presence of metal implants, exposure to ferrous metals either as a vocation or hobby in such a way that unknown embedded metal fragments may cause injury to the subject during exposure to the magnetic field generated during imaging.

Since all subjects will be receiving 2 applications of the radioactive tracer resulting in more than 10 mSv effective dose as part of this study, all subjects must not have been exposed to ionizing radiation as a result of research or radiation treatment procedures during the previous 10 years (§88(2) German Radiation Protection Act), excluding diagnostic procedures (eg, computed tomography).

[REDACTED] and to ensure a reasonable minimum clearance in all subjects through the renal pathway, subjects with a creatinine clearance (calculated by the Cockcroft-Gault formula) <90 mL/min and HD patients with creatinine clearance <60 mL/min will be excluded from the study.

Exposure has been shown to correlate with body weight; therefore, subjects with body weight below 50 kg will be excluded from the study.

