7.4.1. Serum Chemistry, Hematology, and Urinalysis

Clinical laboratory tests (serum chemistry, hematology, coagulation, and urinalysis) will be performed at the time points detailed in [Table 1](#). Clinical laboratory tests will be performed using a central laboratory. Specific laboratory tests to be performed are provided in [Table 5](#).

Table 5: Clinical Laboratory Tests

Serum Chemistry	Hematology and Coagulation	Urinalysis
calcium	hemoglobin	protein
phosphorus	hematocrit	glucose
sodium	red blood cell (RBC) count	ketones
potassium	RBC indices	blood (hemoglobin)
magnesium	platelet count	pH
chloride	white blood cell (WBC) count, and differential count and percentage	specific gravity
glucose	– absolute neutrophil count (ANC)	microscopic
blood urea nitrogen (BUN)	– polymorphonuclear leukocytes (neutrophils)	– bacteria
creatinine (including calculation of creatinine clearance using the Cockcroft-Gault formula)	– lymphocytes	– RBCs
cholesterol (low density lipoprotein (LDL)/high density lipoprotein (HDL) /total)	– eosinophils	– WBCs
uric acid	– monocytes	– casts
alanine aminotransferase (ALT)	– basophils	– crystals
aspartate aminotransferase (AST)	– atypical lymphocytes	
lactate dehydrogenase (LDH)	Prothrombin International Normalized Ratio (INR)	
gamma-glutamyl transpeptidase (GGT)	Activated partial Thromboplastin Time (aPTT)	
alkaline phosphatase		
creatine phosphokinase (CPK) - in case of elevated CPK, the MB fraction should be measured		
total protein		
albumin		
total bilirubin		
direct bilirubin		
indirect bilirubin		
prolactin		

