7.4. Clinical Laboratory Tests

Laboratory test results will be presented in standard international (SI) units. All laboratory data will be listed.

Summary statistics for chemistry, hematology, and urinalysis laboratory tests will be presented for screening, visits 2 and 3, and for the follow-up visit. Summary statistics for coagulation laboratory test will be presented for screening. Laboratory tests values and changes from baseline (absolute) to each visit and time point will be summarized using descriptive statistics.

All values will be compared with predefined criteria, as specified in [Table 1](#), to identify potentially clinically significant values or changes. These values will be listed in the subject data listings. The incidence of potentially clinically significant abnormal values will be summarized for laboratory variables using subject counts as specified in [Section 4.1](#).

Table 1: Criteria for Potentially Clinically Significant Laboratory Values

Test	Criterion value
Serum chemistry	
Alanine aminotransferase (ALT)	$\geq 3 \times$ ULN
Aspartate aminotransferase (AST)	$\geq 3 \times$ ULN
Alkaline phosphatase	$\geq 3 \times$ ULN
Gamma-glutamyl transpeptidase (GGT)	$\geq 3 \times$ ULN
Lactate dehydrogenase (LDH)	$\geq 3 \times$ ULN
Blood urea nitrogen (BUN)	≥ 10.71 mmol/L
Creatinine	≥ 177 μ mol/L
Uric acid Men	≥ 625 μ mol/L
Bilirubin (total)	≥ 34.2 μ mol/L
Hematology	
Hematocrit Men	< 0.37 L/L
Hemoglobin Men	≤ 115 g/L
White blood cell (WBC) counts	$\leq 3 \times 10^9$ /L, $\geq 20 \times 10^9$ /L
Eosinophils	$\geq 10\%$
Absolute neutrophil counts (ANC)	$\leq 1 \times 10^9$ /L
Platelet counts	$\leq 75 \times 10^9$ /L, $\geq 700 \times 10^9$ /L
Urinalysis	
Blood (HGB)	≥ 2 unit increase from baseline
Glucose	≥ 2 unit increase from baseline
Ketones	≥ 2 unit increase from baseline
Total protein	≥ 2 unit increase from baseline

ULN=upper limit of normal range

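### The creatinine-clearance expression printed in HD exclusion r lacks brackets around its denominator and, if evaluated literally, reverses the <60 mL/min criterion (minor)

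*Protocol*

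**What the plan says.** The HD exclusion sets the threshold as "Creatinine clearance <60 mL/min at screening, calculated using the Cockcroft-Gault equation". It then spells the equation out: "calculated using the Cockcroft-Gault equation: $(140 - \text{age}) \times \text{mass (kg)} / 72 \times \text{serum creatinine (mg/dL". Without the typesetting codes this is (140 − age) × mass (kg) / 72 × serum creatinine (mg/dL), on one line, with no brackets after the slash. The same string stands in the Synopsis and in Section 4.2, and the protocol spells the formula out nowhere else.

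Other places name the equation without printing it:
- The healthy-subject exclusion reads "Creatinine clearance <90 mL/min at screening, calculated using the Cockcroft-Gault equation".
- Section 7.4.1 (Table 5) lists, within serum chemistry, "creatinine (including calculation of creatinine clearance using the Cockcroft-Gault formula", and says "Clinical laboratory tests will be performed using a central laboratory".
- Section 4.3 gives the purpose of both thresholds: "to ensure a reasonable minimum clearance in all subjects through the renal pathway".

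**The concern.** An exclusion for clearance below a limit works only if computed clearance falls as kidney function worsens. The documents treat high creatinine as the abnormal direction: SAP Table 1 flags creatinine only at or above an upper limit. In the printed string, creatinine multiplies the rest, so the computed clearance moves the wrong way.

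Anyone who copied the string into a calculator or worksheet would admit HD patients with high creatinine and turn away some with low creatinine. Criterion r is the only numerical renal threshold for these patients, and they are the only group that may receive the 112.5 mg dose (Section 5.1.1).

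**Working it through.** The plan gives no worked clearance value, so there is no figure to reproduce. The check evaluates the printed string and compares it with the bracketed reading.

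**Inputs from the protocol:** the expression and the 60 mL/min threshold (Section 4.2, HD exclusion r); HD patients aged 25 or over with no upper limit and weighing at least 50 kg (Section 4.1).

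**Assumptions:** the ages, weights and creatinine values below. The documents give no distribution for HD patients.

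**Formulas.** Let A = (140 − age) × mass / 72 and S = serum creatinine in mg/dL.
- As printed, in normal order of operations: clearance = A × S.
- Denominator bracketed: clearance = A / S.

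First example: A = 90 × 70 / 72 = 87.5. As printed, 87.5 × 2.0 = 175. Bracketed, 87.5 / 2.0 = 43.8.

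| Assumed patient | A | As printed | Bracketed |
|---|---|---|---|
| 50 y, 70 kg, S 2.0 | 87.5 | 175 (admitted) | 43.8 (excluded) |
| 60 y, 70 kg, S 1.5 | 77.8 | 116.7 (admitted) | 51.9 (excluded) |
| 65 y, 70 kg, S 0.8 | 72.9 | 58.3 (excluded) | 91.1 (admitted) |
| 70 y, 60 kg, S 0.7 | 58.3 | 40.8 (excluded) | 83.3 (admitted) |
| 50 y, 75 kg, S 1.0 | 93.8 | 93.8 (admitted) | 93.8 (admitted) |

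The two values coincide only at S = 1.0, but the eligibility decisions agree over a wider band. As printed, a patient is excluded when S < 60 / A; bracketed, when S > A / 60.
- Age 50, 75 kg (A = 93.75): the printed form excludes S below 0.64 and the bracketed form excludes S above 1.56. Between these, both admit.
- Age 75, 60 kg (A = 54.17): the printed form excludes S below 1.11 and the bracketed form excludes S above 0.90. Between these, both exclude.

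As a range check, both forms were evaluated on an unweighted grid: age 25 to 75 by 5 years, weight 50 to 100 kg by 5 kg, S 0.5 to 3.0 by 0.1, which is 11 × 11 × 26 = 3146 points.
- Of 1804 points with bracketed clearance below 60, the printed form admits 1777.
- Of 1342 points at 60 or above, the printed form excludes 269, of which 213 have bracketed clearance of at least 90.

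These counts show the direction of the error. They are not probabilities, because the grid does not describe real HD patients.

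**The case against.** The strongest reply is that nobody need use the string. The criterion names a known equation and the expression only glosses it. Many readers would take everything after the slash as the denominator, especially beside a below-60 exclusion meant to secure clearance. Section 7.4.1 places the calculation, by the named formula, with central-laboratory chemistry. HD exclusions n (renal disease among serious illnesses) and s (clinically significant abnormal screening laboratory result) offer a second check. The HD cohort is optional and planned at up to 4 patients (Section 9.1).

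Most of this stands and settles the severity. Two parts do not close the point:
- Section 3.14.1 lets routine-care assessments of HD patients made during screening replace the protocol-specific ones, so a site might work from a creatinine value obtained outside the central laboratory.
- Exclusions n and s rest on the investigator's opinion, and neither would restore a patient wrongly excluded under r.

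A flattened fraction in the text extraction is possible but unlikely. The same inline string occurs twice, while the stacked fractions for receptor occupancy and the Emax model survived. A look at the PDF settles it.

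A reader might also infer a unit mismatch, because the expression needs mg/dL and the SAP (Section 7.4) says "Laboratory test results will be presented in standard international (SI) units". That sentence governs how results are presented in the analysis. It does not say which units the screening report uses, so it does not support the inference.

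**Conclusion.** The printed expression is wrong as written in both places, because the missing brackets turn division by creatinine into multiplication. Followed literally, it inverts the criterion outside the band of creatinine values where the two readings give the same decision. For the assumed patient aged 50, weighing 70 kg, with 2.0 mg/dL, the error is 175 against 43.8 mL/min.

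A reader might infer that the trial will admit renally impaired patients. The documents do not support that. They show no calculation made with the string, name the intended equation, and assign the calculation to laboratory chemistry. The consequence is conditional on literal use and confined to the optional HD patients. The healthy-subject threshold of 90 mL/min has no printed formula and is unaffected. No analysis or estimate in the SAP depends on the expression.

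Severity: minor. The conclusion rests on normal operator precedence and on the text extraction being faithful; the patient values are illustrative.

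**What to change.** Reconcile the expression with the equation it names, in the Synopsis and in Section 4.2 (HD exclusion r). Either write (140 − age) × mass (kg) / [72 × serum creatinine (mg/dL)], or delete the expression and cite the named equation alone, as the healthy-subject criterion does. Check that any calculation done at the site matches. Leave the 60 mL/min threshold unchanged.

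The cost is one line in each of two places at the next amendment, plus that check. No SAP change is needed.

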4.3. Justification for Key Inclusion and Exclusion Criteria

The majority of participants enrolled in this study will be healthy subjects; therefore, the inclusion/exclusion criteria established for this trial are those typically utilized to define this population. Due to unknown potential effects of the ^{18}F -tracers on a developing fetus, women have been excluded from participation in the trial, and male subjects must agree to use contraception for the duration of the trial and for 90 days after discontinuation of the study drug.

[REDACTED]

[REDACTED], subjects with current or history of a heart condition or increased pro-arrhythmic risk, epilepsy or seizures within the last 5 years, and clinically significant psychiatric diseases such as major depressive disorder or anxiety are to be excluded from participation in this study.

All subjects participating in this study will receive multiple scans (MRI and PET); therefore, individuals with a history of claustrophobia will be excluded from participation in this study. Additionally, subjects may not have contraindications to MRI such as the presence of metal implants, exposure to ferrous metals either as a vocation or hobby in such a way that unknown embedded metal fragments may cause injury to the subject during exposure to the magnetic field generated during imaging.

Since all subjects will be receiving 2 applications of the radioactive tracer resulting in more than 10 mSv effective dose as part of this study, all subjects must not have been exposed to ionizing radiation as a result of research or radiation treatment procedures during the previous 10 years (§88(2) German Radiation Protection Act), excluding diagnostic procedures (eg, computed tomography).

[REDACTED] and to ensure a reasonable minimum clearance in all subjects through the renal pathway, subjects with a creatinine clearance (calculated by the Cockcroft-Gault formula) <90 mL/min and HD patients with creatinine clearance <60 mL/min will be excluded from the study.

Exposure has been shown to correlate with body weight; therefore, subjects with body weight below 50 kg will be excluded from the study.

4.4. Withdrawal Criteria and Procedures

In accordance with the Declaration of Helsinki (in accordance with the applicable country's acceptance), each subject is free to withdraw from the study at any time. The investigator also has the right to withdraw a subject from the study in the event of intercurrent illness, adverse events, or other reasons concerning the health or well-being of the subject, or in the event of lack of cooperation. In addition, a subject may be withdrawn from the study drug treatment as described in Sections [3.12](#), [3.14.4](#), and [7.1.7](#).

Should a subject decide to withdraw after administration of study drug(s), or should the investigator decide to withdraw the subject, all efforts will be made to complete and report all observations up to the time of withdrawal. A complete final evaluation at the time of the subject's withdrawal should be made and an explanation given as to why the subject is withdrawing or being withdrawn from the study.

The reason for and date of withdrawal from study drug treatment and the reason for and date of withdrawal from the study must be recorded on the source documentation and transcribed to the CRF. If a subject withdraws consent, every attempt will be made to determine the reason. If the reason for withdrawal is an adverse event or a clinically significant abnormal laboratory test result, monitoring will be continued at the discretion of the investigator (eg, until the event has resolved or stabilized, until the subject is referred to the care of a health care professional, or until a determination of a cause unrelated to the study drug or study procedure is made). The specific event or test result must be recorded on the source documentation and transcribed to the CRF.

